# 9.9 Medical, Ocular and Dry Eye History

Medical history terms and ocular history terms will be coded using the Medical Dictionary for Regulatory Activities (MedDRA) version 24.0 and the number and percent of subjects with medical history will be summarized by (SOC) and Preferred Term (PT) for each treatment group based on the safety population.

# 9.10 Treatment Exposure

Each randomized subject will receive an application of OC-01 (varenicline) Nasal Spray or placebo three times daily (TID) for 8 weeks. Duration of exposure to study treatment, in days, will be summarized for all safety subjects. Summary statistics for duration of exposurewill be presented by treatment group.

#### 9.11 Ocular Assessments

Ocular assessments will occur at baseline and different study visits. The results, grade, clinical significance, and relatedness to administration procedure and study drug, will belisted, summarized in tables, and presented in figures as appropriate.

# 9.11.1 Schirmer's Test with Topical Anesthesia

The Schirmer's Test without topical anesthetic will be performed to assess tear production at the Screening Visit (Visit 1). Additional Schirmer's Test with topical anesthetic will be assessed after the first treatment at Visit 1. At Week 1 (Visit 2) and Week 8 (Visit 6) and/or at the time of early termination, the Schirmer's Tests will be performed concurrent with treatment.

# 9.11.2 Pain Visual Analog Scale (VAS)

The Pain Visual Analog Scale (VAS) will be performed at Screening (Visit 1), Week 2 (Visit3), Week 4 (Visit 4), Week 6 (Visit 5), Week 8 (Visit 6). At post-treatment visit, change in VAS from pre- to post-treatment will be collected and summarized by treatment group for both study and fellow eyes.

#### 9.11.3 Early Treatment Diabetic Retinopathy Study (ETDRS) BCDVA

Best corrected distance visual acuity (BCDVA) will be performed and collected at Screening (Visit 1), Week 4 (Visit 4), and Week 8 (Visit 6).

On the BCDVA Assessment CRF Form, the total number of letters read correctly in each row of letters should be written down. Visual acuity will be measured once for each eye, using Chart 1 for the right eye, Chart 2 for the left eye, and Chart 1 for binocular vision testing.

After each measurement of visual acuity, the visual score for the visit is calculated. The visual acuity score is defined as follows:

- If 20 or more letters are read correctly at the 4-meter test distance, the visual acuity score is equal to the numbers of letters read correctly at 4 meters, plus 30; or
- If less than 20 letters are read correctly at the 4-meter test distance, the visual acuity score is equal to the number of letters read correctly at 1 meter plus the number at 4 meters: or
- If no letters are read correctly at either the 4-meter distance or the 1-meterdistance, the visual acuity score is 0.

BCDVA will be summarized by visit and by treatment group for both study and fellow eyes. The change from baseline in BCDVA will be calculated. The descriptive statistics for the treatment difference in change from baseline will be presented. In addition, 95% confidence interval in treatment difference will be presented as well.

# 9.11.4Corneal Sensitivity

Corneal sensitivity will be performed at Screening (Visit 1, prior to Schirmer's Test), Week 4(Visit 4), and Week 8 (Visit 6).

Corneal sensation is measured in the affected eye of the patient at all applicable visits using a Cochet Bonnet aesthesiometer. The measurements taken from the affected eye are as follows: Sensitivity in each of the 4 quadrants of the cornea:

- Superior nasal (cm)
- Inferior nasal (cm)
- Superior temporal (cm)

• Inferior temporal (cm)

Steps for using the handheld aesthesiometer:

Note: Cochet Bonnet aesthesiometer measurements MUST be performed prior toadministration of Topical Anesthesia.

- Sterilize the filament.
- Extend the filament to full length of 6 cm.
- Perform sensitivity in each of the 4 quadrants of the cornea:
- Superior nasal (cm)
- Inferior nasal (cm)
- Superior temporal (cm)
- Inferior temporal (cm)
- Retract the filament incrementally in 0.5 cm steps until the patient can feel its contact.
- Record the length (NOTE: The shorter the length indicates decreased sensation.)
- Compare the fellow eye cornea.
- Repeat steps 1-4 in each quadrant: superior, temporal, inferior, nasal.
- Sterilize the filament and retract back into the device to protect it from damage.

For Stage 1 subjects, corneal sensitivity is defined as the mean of the 4 quadrants (four measurements).

The superior nasal, inferior nasal, superior nasal, inferior temporal, sensitivity within the area of PED, and mean score will be calculated at each visit. Corneal sensitivity results will be summarized for each treatment group for the study and fellow eyes by visit using discrete summary statistics.

#### 9.11.5 Corneal Fluorescein Staining

Corneal fluorescein staining will be performed, and data will be collected at Screening (Visit1, prior to Schirmer's Test), Week 1 (Visit 2), Week 2 (Visit 3), Week 4 (Visit 4), and Week8 (Visit 6). Corneal fluorescein staining will be assessed for both the study and fellow eyes. The examiner compares the overall appearance of the patient's corneal staining with the Modified Oxford Grading Scale and selects the appropriate grade that best represents the state of corneal staining. The corneal fluorescein staining score will be described by visit, treatment, study eye, and fellow eye with summary statistics.

# 9.11.6Slit Lamp Biomicroscopy

The slit lamp biomicroscopy will be performed at Screening (Visit 1, prior to Schirmer's Test), Week 1 (Visit 2), Week 2 (Visit 3), Week 4 (Visit 4), and Week 8 (Visit 6). A slit lampwill be used for external examination and biomicroscopy. The cornea, conjunctiva, anterior chamber, iris, eyelid, motility, pupil, and lens will be examined at each visit. Slit lamp biomicroscopy results will be summarized for each treatment group for the study and fellow eyes by visit using discrete summary statistics. Abnormal clinically significant findings will be described. Shifts from baseline including normal to abnormal

(not clinically significant), and normal to abnormal (clinically significant) will be presented using counts and percentages.

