# 5.3. Inclusion Criteria

#### Subjects must:

- 1. Be at least 18 years of age at Visit 1.
- 2. Patients with Stage 1 (corneal epithelial hyperplasia/punctate keratopathy) NK- in one or both eyes, as defined by the Mackie Criteria.
- 3. Evidence of decreased corneal sensitivity ( $\leq 4$  cm using the Cochet-Bonnet aesthesiometer) in at least 1 corneal quadrant.

[figure not shown]

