# **Slit Lamp Bio microscopy**

Slit lamp bio microscopy will be performed during the study. Observations will be graded as *Normal* or *Abnormal*. Abnormal findings, which are clinically significant, will be described.

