#### 5.3 Exploratory Efficacy Endpoint

- Percent of subjects who achieve ≥ 3 lines (15 letters) of improvement in ETDRS visual acuity at Week 8.
- Percent of subjects who achieve complete resolution of corneal staining will be the exploratory endpoint. Complete resolution of corneal staining will be the exploratory endpoint is defined as complete resolution of corneal staining (0 mm lesion and no residual staining) in subjects with Stage 1 NK at Week 8.
- Percentage (%) of subjects that progress to Stage 2 Persistent Epithelial Defect (PED) NKat Week 8.
- Improvement in corneal sensitivity at Week 8
- Mean change from baseline in corneal fluorescein staining in subjects with Stage 2 NK at Week 8.
- Schirmer's score with topical anesthesia
- Pain visual analog scale (VAS)
- Slit lamp biomicroscopy
- NEI-VFQ-25 Survey

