#### 10 Intranasal Examination

Intranasal assessments collected at Screening (Visit 1), Week 1 (Visit 2), Week 2 (Visit 3), Week 4 (Visit 4), Week 6 (Visit 5), Week 8 (Visit 6), and Week 24 (Visit 8) will be summarized by treatment group with counts and percentages. Shifts from baseline of normal to abnormal (not clinically significant) and normal to abnormal (clinically significant) will be presented using counts and percentages.

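### The intranasal shift table as specified omits worsening from an abnormal baseline, and the named slit lamp shifts are expected to be nearly empty for study-eye corneas

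*SAP*

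**What the plan says.** SAP 9.11.6 (Slit Lamp Biomicroscopy) introduces its shift table with "Shifts from baseline including normal to abnormal" and completes the list with "not clinically significant), and normal to abnormal (clinically significant) will be presented using counts and percentages". Two shifts are named, both starting from normal. The word *including* leaves the list open.

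SAP 10 (Intranasal Examination) names the same two shifts without that opening word: "Shifts from baseline of normal to abnormal (not clinically significant) and normal to abnormal (clinically significant) will be presented using counts and percentages".

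SAP 9.11.6 also plans slit lamp results by arm, eye and visit, covers eight structures of which the cornea is one, and says that clinically significant abnormal findings are described. Protocol Appendix 2 has the same provision: "Abnormal findings, which are clinically significant, will be described". SAP 10 plans intranasal counts and percentages by arm for visits through Week 24.

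Protocol 5.3 admits "Patients with Stage 1 (corneal epithelial hyperplasia/punctate keratopathy) NK- in one or both eyes". Protocol 6.2 lists three safety measures: adverse events, the intranasal examination and slit lamp biomicroscopy. SAP 5.3 also lists "Slit lamp biomicroscopy" among the exploratory efficacy endpoints. Protocol 10.5.7 provides for changes or shifts where appropriate, does not restrict them to a normal baseline, and leaves the detail to the SAP.

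**The concern.** A shift table shows what happened to each subject relative to that subject's own baseline. If it has rows only for subjects who start normal, it is silent about anyone who starts abnormal.

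For the nose, the product is given intranasally, and Protocol Appendix 2 says that the examination is there to monitor mucosal integrity. The exclusion examples given there are severe or structural findings, so a minor abnormality at entry appears admissible. Part of the exclusion list is not visible, so this is not certain. Such a subject who becomes clinically abnormal on treatment would appear in no shift row.

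For the cornea, the disease under study is itself a corneal epithelial abnormality. A programmer who builds only the named rows would get a study-eye corneal table with counts near zero in both arms, whether or not corneas changed. Read alone, that table could be mistaken for reassurance.

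The omission also fits poorly with the plan's own idea of harm. Protocol 9.1 and SAP 15.1 treat worsening of an existing condition as an event alongside new onset. The named shifts cover only new onset.

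**Working it through.** The plan gives no figure to reproduce. The check is a count of cells and a comparison of passages.

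**Step 1: possible changes.** The SAP's shifts use three grades: normal, NCS and CS. Baseline by visit gives 3 × 3 = 9 cells. Three are no change, so 9 − 3 = 6 are changes.

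| Baseline to visit | Direction | Named in SAP 9.11.6 and SAP 10? |
|---|---|---|
| Normal to NCS | worse | yes |
| Normal to CS | worse | yes |
| NCS to CS | worse | no |
| NCS to normal | better | no |
| CS to NCS | better | no |
| CS to normal | better | no |

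Named: 2 of 6 changes, 2 of 3 worsenings, 0 of 3 improvements, and 0 of the 4 changes that start from an abnormal grade.

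**Step 2: study-eye corneas that can enter a named shift.** Protocol 5.1 plans about 50 subjects per arm. If k of 50 study-eye corneas are graded abnormal at baseline, at most 50 − k can enter a named shift. If all are abnormal (k = 50), that is 50 − 50 = 0 per arm. A full table would place all of about 50.

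That k is close to 50 is inferred. Protocol 5.3 requires Stage 1 disease and characterises it by corneal epithelial findings. The per-protocol population, on which the primary analysis runs, also requires baseline staining of at least 2 (Protocol 10.2.2 and 10.5.5; SAP 14.1). No section says that the baseline slit lamp grade of the cornea must be abnormal.

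**Step 3: where the named shifts still work.** Seven of the eight slit lamp structures (8 − 1 = 7) and fellow-eye corneas that are normal at baseline can enter them. Nothing in the entry criteria makes noses abnormal, so the named nasal shifts may cover most subjects. The documents give no rate of abnormal nasal baselines.

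**Step 4: whether the by-visit counts fill the gap.** Two illustrations with 50 corneas in an arm:

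- 10 move from NCS to CS and nobody else changes. The by-visit CS count rises by 10, so the marginal summary shows it.
- 10 move from NCS to CS and 10 from CS to NCS. The CS count changes by +10 − 10 = 0, and so does the NCS count. The marginal summary shows nothing, while a within-subject table shows 10 worsened and 10 improved.

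By-visit counts thus show net movement and can hide offsetting movement.

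**The case against.** The strongest reply is that the plan already reports deterioration in several ways. SAP 9.11.6 gives slit lamp categories by arm, eye and visit and describes clinically significant findings. Staining grade (SAP 9.11.5) and Mackie stage (SAP 12) follow the cornea over visits. Worsening of an existing condition counts as an adverse event, and Protocol 10.5.7 makes adverse events the main safety assessment. All collected data are also listed by subject and visit. This stands, and it limits the gap to the within-subject cross-tabulation. It does not close it: marginal counts can offset, and Table 1 in Protocol Appendix 2 puts neovascularization and scarring within Stage I, so a cornea can change without changing stage.

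Four stronger readings are tempting, and the documents do not support them.

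- *The slit lamp table cannot show corneal worsening or improvement.* The word *including* leaves other shifts open, and Protocol 10.5.7 does not confine shifts to a normal baseline. The slit lamp defect is incomplete specification.
- *Every study cornea is certain to be graded abnormal.* This is very likely but inferred. Some Stage I findings in Table 1 are not corneal, and the per-protocol staining threshold implies that some subjects may enter with a score below 2.
- *The nasal table fails for the same reason.* The diseased-cornea argument has no bearing on the nose. The nasal point rests only on the closed wording of SAP 10.
- *Improvement goes unanalysed although the slit lamp is an efficacy endpoint.* The endpoint is exploratory, and only the heading of SAP 14.3, where its analysis would belong, is visible. This cannot be judged.

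**Conclusion.** The point holds in limited form. As written, SAP 10 omits nasal worsening from NCS to CS from its shift table. SAP 9.11.6 leaves the list open, but the two shifts it names are expected to be nearly empty for study-eye corneas: about 0 of 50 per arm if all are abnormal at baseline. That figure rests on the inference from Stage 1 entry. The size of the nasal gap depends on how many subjects enter with a nasal abnormality, which the documents do not say.

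What is missing is the within-subject shift in two descriptive safety outputs. No hypothesis test depends on it, and the primary analysis is unaffected. It is worth correcting because the better display is concrete and cheap, and because slit lamp and intranasal examination are two of the three named safety measures.

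**What to change.** In SAP 9.11.6 and SAP 10, replace the two named shifts with a full three-by-three shift table: baseline normal, NCS or CS against the same grades at each visit and at the worst post-baseline assessment. For the slit lamp, present it by structure and separately for study and fellow eyes. Define worsened as any move to a higher grade, and state that NCS to CS is included.

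The cost is SAP wording and table shells. The shifts already named need the same three grades, so the fuller table asks for no new data. The change is best made before unmasking.

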#### 10 Intranasal Examination

Intranasal assessments collected at Screening (Visit 1), Week 1 (Visit 2), Week 2 (Visit 3), Week 4 (Visit 4), Week 6 (Visit 5), Week 8 (Visit 6), and Week 24 (Visit 8) will be summarized by treatment group with counts and percentages. Shifts from baseline of normal to abnormal (not clinically significant) and normal to abnormal (clinically significant) will be presented using counts and percentages.

#### 11 NEI-VFQ-25 Survey

The National Eye Institute (NEI) sponsored the development of the VFQ-25 with the goal of creating a survey that would measure the dimensions of self-reported vision-targeted health status that are most important for patients who have chronic eye diseases. Questions included in the VFQ25 represent the content identified during a series of condition-specific focus groups with patients who had age-related cataracts, glaucoma, age-related macular degeneration, diabetic retinopathy, or CMV retinitis.

The VFQ-25 consists of a base set of 25 vision-related questions representing 11 vision- targeted constructs, plus an additional single-item general health rating question. Table 1 presents the 11 vision-targeted items and the health-related item and their correspondent question numbers.

Table 1 Averaging of Items to Generate VFQ-25 Sub-Scales				
Scale	Number of items	Items to be averaged		
General Health	1	1		
General Vision	1	2		
Ocular Pain	2	4, 19		
Near Activities	3	5, 6, 7		
Distance Activities	3	8, 9, 14		
Vision Specific:				
Social Functioning	2	11, 13		
Mental Health	4	3, 21, 22, 25		
Role Difficulties	2	17, 18		
Dependency	3	20, 23, 24		
Driving	3	15c, 16, 16a		
Color Vision	1	12		
Peripheral Vision	1	10		

Scoring VFQ-25 with or without optional items is a two-step proces

First, original numeric values from the survey are re-coded following the scoring rules outlined in Table 2. All items are scored so that a high score represents better functioning. Each item is then converted to a 0 to 100 scale so that the lowest and highest possible scores are set at 0 and 100 points, respectively.

Table 2. Scoring Key: Recording of Items				
Item Numbers	Change original response category (a)	To recorded value		
	1	100		
	2	75		
$1, 3, 4, 15c^{(b)}$	3	50		
	4	25		
	5	0		
	1	100		
	2	80		
	3	60		
2	4	40		
	5	20		
	6	0		
	1	100		
	2	75		
5 6 7 0 0 10 11 12 12 14 16 16	3	50		
5, 6, 7, 8, 9, 10, 11, 12, 13, 14, 16, 16a	4	25		
	5	0		
	6	*		
	1	0		
	2	25		
17, 18, 19, 20, 21, 22, 23, 24, 25	3	50		
	4	75		
	5	100		

a) Precoded response choices as printed in the questionnaire.

Note: If 15b=1, then 15c should be recoded to "0"

If 15b=3, then 15c should be recoded to missing.

Second, items within each sub-scale are averaged together to create the 12 sub-scale scores. Table indicates which items contribute to each specific sub-scale. Items that are left blank (missing data) are not taken into account when calculating the scale scores. Sub-scales with at least one item answered can be used to generate a sub-scale score. Hence, scores represent the average for all items in the subscale that the respondent

b) Item 15c has four-response levels, but is expanded to a five-levels using item 15b.

If 15b=2, then 15c should be recoded to missing.

\* Response choice "6" indicates that the person does not perform the activity because of non-vision related problems. If this choice is selected, the item is coded as "missing."

Table 3. Averaging of Items to Generate VFQ-25 Sub-Scales					
		Items to be averaged (after			
Scale	Number of items	recording per Table 2)			
General Health	1	1			
General Vision	1	2			
Ocular Pain	2	4, 19			
Near Activities	3	5, 6, 7			
Distance Activities	3	8, 9, 14			
Vision Specific:					
Social Functioning	2	11, 13			
Mental Health	4	3, 21, 22, 25			
Role Difficulties	2	17, 18			
Dependency	3	20, 23, 24			
Driving	3	15c, 16, 16a			
Color Vision	1	12			
Peripheral Vision	1	10			

Descriptive statistics for the NEI-VFQ-25 Survey collected at Screening (Visit 1), Week 4 (Visit 4), and Week 8 (Visit 6), and their change from baseline will be provided by treatmentgroup and analysis visit based on ITT population.

# 12 NK Staging per Mackie Criteria

NK Staging per Mackie Criteria collected at Week 1 (Visit 2), Week 2 (Visit 3), Week 4 (Visit 4), Week 6 (Visit 5), and Week 8 (Visit 6) will be summarized by treatment group witheach staging counts and percentages.

# 13 In-vivo Confocal Microscopy

In-vivo Confocal Microscopy will be listed by subjects ID and visit or visit date.

# 14 Efficacy Analysis

the primary efficacy endpoint as well as the secondary endpoints, the significance level

the primaryefficacy endpoint as well as the secondary endpoints, the significance level of 5% will be used for all the testing hypotheses and no multiple comparison adjustment will be performed.

# 14.1 Primary Efficacy Endpoints

[figure not shown]

[figure not shown]
The primary endpoint will be the mean change from baseline in cornstaining at Week 8. The primary efficacy endpoint will be analyzed on the PP population using an analysis of covariance model comparing the treatment group to placebo with the randomization strata, baseline Schirmer's Test Score and the baseline corneal fluorescein staining as the covariates.

#### 14.2 Secondary Efficacy Endpoint

The secondary efficacy endpoint is the mean change from baseline in ETDRS visual acuity at Week 8. The secondary efficacy endpoint will be analyzed on the PP population using an analysis of covariance model comparing the treatment group to placebo with the randomization strata, baseline Schirmer's Test Score and the baseline ETDRS visual acuity as the covariates.

## 14.3 Exploratory endpoints

## 14.4 Missing Efficacy Data Handling

# 15 Safety Analysis

The safety population will be used for all safety analyses. All recorded safety parameters willbe listed by treatment, subjects ID and visit or visit date.

#### 15.1 Adverse Events

The investigator will promptly review each Adverse Event (AE) for accuracy and completeness, and classify each AE according to its intensity, its relationship to study drug oradministration procedure, and its seriousness. AEs will be coded using version 24.0 of the MedDRA dictionary. AEs will be monitored throughout the study and documented on the appropriate AE form. AEs will be categorized as ocular and non-

ocular events as well as by system organ class (SOC) and preferred term (P1), seriousness, severity, and relation to study medications.

All treatment-emergent adverse events (TEAEs) will be summarized. TEAE is defined as an AE that is new or worsened in severity compared to the first dose of study drug. All AEs willbe presented in data listing with a flag indicating the event is a TEAE.

TEAEs will be summarized by subject level. In addition, the number of TEAE episodes that occurred during the study will be provided in the overall summary of AE table.

The following presentations of TEAEs will be generated:

- Overall adverse events summary (including any TEAEs, ocular TEAEs, non-ocularTEAEs, resolved ocular TEAEs, ocular TEAEs, non-ocular TEAEs, treatment- emergent SAEs, treatment-related treatment emergent SAEs, TEAEs by maximum severity, TEAEs related to study drug, AEs leading to treatment/study discontinuation, TEAEs leading to death);
- All ocular TEAEs by SOC and PT;
- All non-ocular TEAEs by SOC and PT;
- All TEAEs by Severity, SOC, and PT;
- All TEAEs by Relationship to Study Drug, SOC, and PT;
- Serious TEAEs by SOC and PT;
- Serious TEAEs related to Study Drug by SOC and PT;
- TEAEs leading to treatment discontinuation;
- TEAEs leading to study discontinuation;
- TEAEs leading to death.

